7.0 TRIAL PROCEDURES

7.1 Trial Procedures

The Trial Flow Chart - Section 6.0 summarizes the trial procedures to be performed at each visit. Individual trial procedures are described in detail below. It may be necessary to perform these procedures at unscheduled time points if deemed clinically necessary by the investigator.

Furthermore, additional evaluations/testing may be deemed necessary by the investigator and or the Sponsor for reasons related to subject safety. In some cases, such evaluation/testing may be potentially sensitive in nature (e.g., HIV, Hepatitis C, etc.), and thus local regulations may require that additional informed consent be obtained from the subject. In these cases, such evaluations/testing will be performed in accordance with those regulations.

7.1.1 Administrative Procedures

7.1.1.1 Informed Consent

The investigator or qualified designee must obtain documented consent from each potential subject or each subject's legally acceptable representative prior to participating in a clinical trial or Future Biomedical Research. If there are changes to the subject's status during the trial (e.g., health or age of majority requirements), the investigator or qualified designee must ensure the appropriate consent is in place.

7.1.1.1.1 General Informed Consent

Consent must be documented by the subject's dated signature or by the subject's legally acceptable representative's dated signature on a consent form along with the dated signature of the person conducting the consent discussion.

A copy of the signed and dated consent form should be given to the subject before participation in the trial.

The initial informed consent form, any subsequent revised written informed consent form and any written information provided to the subject must receive the IRB/ERC's approval/favorable opinion in advance of use. The subject or his/her legally acceptable representative should be informed in a timely manner if new information becomes available that may be relevant to the subject's willingness to continue participation in the trial. The communication of this information will be provided and documented via a revised consent form or addendum to the original consent form that captures the subject's dated signature or by the subject's legally acceptable representative's dated signature.

Specifics about a trial and the trial population will be added to the consent form template at the protocol level.

The informed consent will adhere to IRB/ERC requirements, applicable laws and regulations and Sponsor requirements.

7.1.1.1.2 Consent and Collection of Specimens for Future Biomedical Research

The investigator or qualified designee will explain the Future Biomedical Research consent to the subject, answer all of his/her questions, and obtain written informed consent before performing any procedure related to the Future Biomedical Research sub-trial. A copy of the informed consent will be given to the subject.

7.1.1.2 Inclusion/Exclusion Criteria

All inclusion and exclusion criteria will be reviewed by the investigator or qualified designee to ensure that the subject qualifies for the trial.

7.1.1.3 Subject Identification Card

All subjects will be given a Subject Identification Card identifying them as participants in a research trial. The card will contain trial site contact information (including direct telephone numbers) to be utilized in the event of an emergency. The investigator or qualified designee will provide the subject with a Subject Identification Card immediately after the subject provides written informed consent. At the time of treatment allocation/randomization, site personnel will add the treatment/randomization number to the Subject Identification Card.

The subject identification card also contains contact information for the emergency unblinding call center so that a health care provider can obtain information about trial medication/vaccination in emergency situations where the investigator is not available.

7.1.1.4 Medical History

A medical history will be obtained by the investigator or qualified designee.

7.1.1.5 Prior and Concomitant Medications Review

7.1.1.5.1 Prior Medications

The investigator or qualified designee will review prior medication use, including any protocol-specified washout requirement, and record prior medication taken by the subject within 30 days before starting the trial.

7.1.1.5.2 Concomitant Medications

The investigator or qualified designee will record medication, if any, taken by the subject through 2 weeks after the study treatment period. The investigator or qualified designee will discuss with the subject the necessity of not taking any concomitant medications or herbal preparations with known suspected hepatotoxic potential. If medications with potential hepatotoxicity cannot be discontinued in a subject, the investigator or qualified designee must discuss the inclusion of the subject with the Sponsor's clinical director who must approve the use of the medication prior to inclusion of the subject in the trial. To minimize the risk of adverse drug interactions, every effort should be made to limit the number of concomitant drugs to those that are truly essential. Non-study HCV medications/therapies are prohibited through FW24. Any use should be reported throughout the subject's participation in the trial.

7.1.1.6 Assignment of Screening Number

All consented subjects will be given a unique screening number that will be used to identify the subject for all procedures that occur prior to randomization or treatment allocation. Each subject will be assigned only one screening number. Screening numbers must not be re-used for different subjects.

Any subject who is screened multiple times will retain the original screening number assigned at the initial screening visit.

Specific details on the screening visit requirements (screening/rescreening) are provided in Section 7.1.5.

7.1.1.7 Assignment of Treatment/Randomization Number

All eligible subjects will be randomly allocated and will receive a treatment/randomization number. The treatment/randomization number identifies the subject for all procedures occurring after treatment allocation/randomization. Once a treatment/randomization number is assigned to a subject, it can never be re-assigned to another subject.

A single subject cannot be assigned more than 1 treatment/randomization number.

7.1.1.8 Trial Compliance (Medication)

The investigator/study coordinator will give the subject a Study Medication Diary (SMD) to be completed during the study period. The investigator/study coordinator will be responsible for entering the subject's identification (treatment/randomization number), treatment period, and other pertinent subject information before giving the SMD to the subject. The subject will be instructed to record dates/times and the number of tablets/capsules of study drug doses (Note: RBV is a rescue medication and should be reported as a concomitant medication; it should not be reported on the SMD.) on the SMD for the entire time period. Only the subject should enter information on the SMD. The subject is to return the completed SMD at each scheduled visit. At all visits during the treatment period, site personnel must verify the accuracy of the SMD by comparing entries with amounts of unused study drug. If a discrepancy is noted, investigator/study coordinator must discuss the discrepancy with the subject, and the explanation must be documented. Only the subject shall make any changes to the entries on the SMD. The subject will initial the SMD to confirm that the information is accurate. The investigator/study coordinator will be responsible for transferring the appropriate information from the diary onto the appropriate case report form (CRF).

Interruptions from the protocol specified treatment plan, as outlined in Section 5.2, require consultation between the investigator and the Sponsor and written documentation of the collaborative decision on subject management.

Administration of trial medication will be witnessed by the investigator and/or trial staff at the Day 1 visit.

7.1.2 Clinical Procedures/Assessments

7.1.2.1 Physical Examination

All physical examinations must be performed by the principal investigator or sub-investigator (physician, physician assistant, or nurse practitioner).

A complete physical examination, performed at the Screening visit, includes the following assessments: general appearance, head, eyes, ears/nose/throat, neck, lymph nodes, skin, lungs, heart, abdomen, musculoskeletal, and neurologic evaluations. Breast, rectal, and genitourinary/pelvic examinations should be performed when clinically indicated. For all other visits, a focused physical examination will be performed when clinically indicated. Any significant changes between the screening visit and other physical examinations performed prior to the initiation of therapy should be noted in the Medical History electronic CRF (eCRF). Any significant changes after receiving study drug at Day 1 must be reported as AEs and entered on the AE eCRF. If a subject is discontinued for any reasons during the treatment period, every attempt should be made to perform a final physical examination.

7.1.2.2 Weight and Height Assessment

The subject's weight and height should be assessed as mentioned in the Trial Flow Chart (Section 6.0). Clinically significant changes from Day 1 in weight should also be captured as AEs in the eCRF.

7.1.2.3 12-Lead ECG

Special care must be taken for proper lead placement. Subjects should be shaved as necessary for proper lead placement. Subjects should be resting in a semi-recumbent position for at least 10 minutes prior to having ECG readings obtained. However, clinically significant findings from the screening ECG must be captured in the medical history eCRF. For ECGs performed during treatment or during the follow-up period, any clinically significant changes compared with the screening ECG must be captured as AEs.

All subjects will have 12-lead ECGs performed at screening, Day 1, TW2, TW4, TW8, TW12, FW4, and FW12. In addition, the subset of subjects in the Intensive PK/PD group will also have 12-lead ECGs performed at Day 3 and Day 7.

7.1.2.4 Vital Signs

Vital signs will include heart rate, blood pressure, and oral temperature. Subjects should be resting in a semi-recumbent or sitting position for at least 10 minutes prior to having vital sign measurements obtained.

Oral temperatures should be taken, but if oral is not possible, a tympanic, rectal, or axillary temperature may be taken (note: temporal is allowed).

After the screening visit, the site should indicate whether or not the result is clinically significant and if any subsequent changes constitute an AE.

7.1.2.5 Birth Control Confirmation

Care must be taken to avoid pregnancy in female subjects of childbearing potential, and for the female partners of childbearing potential of male subjects, who have their treatment regimen with MK-3682 + RZR extended to 16 weeks' duration and RBV added to the regimen.

Confirmation must be obtained by site personnel that subjects and their partner(s) are using acceptable methods of contraception (see Subject Inclusion Criteria, Section 5.1.2). This assessment must be documented in the subject's study chart at each specified visit (see Trial Flow Chart, Section 6.0).

7.1.2.6 Adverse Events

Refer to Section 7.2 for details on assessing and recording AEs.

7.1.2.7 Noninvasive Methods of Cirrhosis Evaluation

FibroScan[®]: This method for assessing liver cirrhosis has gained increasing acceptance. In the US, this methodology is Food and Drug Administration (FDA) approved and, in other countries, it is often the preferred method of assessment. FibroScan[®] results are influenced by a number of confounders including ALT, ascites, and underlying disease. Hepatitis C is one of the best studied and is the disease state with the most reproducible/reliable results. FibroScan[®] has been evaluated in many liver diseases for the staging of liver fibrosis, and has been demonstrated to be very effective for differentiating cirrhosis (F4) from no cirrhosis (<F4), but it is less capable of differentiating gradations of fibrosis. In a large study by Castera, et al [40], a population of patients with chronic HCV infection, a cutoff of 12.5 kPa was selected for cirrhotics. At this cutoff, the sensitivity and specificity of the test for cirrhosis were 87% and 91%, respectively, and the negative predictive value was 95%. Since this analysis was assessed specifically in subjects with chronic HCV infection, the cutoff value >12.5 kPa used by Castera was selected to include cirrhotics in the current study.

FibroTest[®] + APRI: Various methodologies have been developed in order to improve the sensitivity and specificity of blood tests used to diagnose cirrhosis in patients with chronic HCV infection. One such algorithm, the sequential algorithm for fibrosis evaluation (SAFE), which uses a combination of FibroTest[®] and the APRI, is very accurate for diagnosing cirrhosis [41]. For cirrhosis, the SAFE for F4 algorithm provides a diagnostic accuracy of 89.5% with a negative predictive value of 94.6%. Using this algorithm, it is estimated that only 6.2% of the patients would need a liver biopsy to confirm the diagnosis of cirrhosis. The cutoff values for excluding cirrhotics using the 2 tests, without the use of liver biopsy, are ≤ 1 and ≤ 0.48 for FibroTest[®] and APRI when the SAFE for F4 is used. This study uses this method with one variation, which is the more stringent requirement that both the APRI and FibroTest[®] need to be consistent with no cirrhosis (i.e., APRI is ≤ 1 AND FibroTest[®] ≤ 0.48).

7.1.3 Laboratory Procedures/Assessments

Details regarding specific laboratory procedures/assessments to be performed in this trial are provided below (see Table 12). The total amount of blood/tissue to be drawn/collected over the course of the trial (from pre-trial to post-trial visits), including approximate blood/tissue

volumes drawn/collected by visit and by sample type per subject can be found in Section 12.3.

7.1.3.1 Laboratory Safety Evaluations (Hematology, Chemistry and Urinalysis)

Laboratory tests for hematology, chemistry, and urinalysis are specified in [Table 12](#). Sample collection, storage and shipment instructions will be provided in the operations/laboratory manual.

Table 12 Laboratory Tests

Hematology	Chemistry	Urinalysis	Other
Hematocrit	Albumin	Bilirubin	HCV GT
Hemoglobin	ALP	Blood	HIV-1 and HIV-2 serology (screening only)
Platelet count	ALT	Glucose	PT/INR
WBC (total and differential)	AST	Ketone	PTT
Erythrocytes (RBC count)	Creatinine	Leukocyte esterase	Choriogonadotropin beta (Urine pregnancy test kits to sites)
	Creatinine clearance (eGFR)	Nitrites	Serum human chorionic gonadotropin (reflex when urine pregnancy test is “positive”)
	Creatine kinase	pH	Plasma HCV RNA
	Gamma-glutamyltransferase	Protein	Fibrosure [®] (Fibrotest) as requested by site for entry criteria (may be performed locally)
	Glucose (serum glucose)	Specific gravity	APRI calculation (screening only)
	Amylase	Bacteria	CD4+ T-cell count (at screening in all subjects, then in HIV/HCV coinfecting subjects only at subsequent visits)
	Lipase	Squamous epithelial cells	Plasma HIV-1 RNA (at screening in all subjects, then in HIV/HCV coinfecting subjects only at subsequent visits)

Hematology	Chemistry	Urinalysis	Other
	Potassium	RBC	HBsAg (at screening in all subjects, then at certain subsequent visits for subjects who are anti-HBc positive)
	Sodium	WBC	Anti-HBc (screening only)
	Total bilirubin		Anti-HBs (screening only)
	Direct bilirubin		HBV DNA (for subjects who are anti-HBc positive, at screening and at certain subsequent visits)
	Indirect bilirubin		
	Total protein		
	Blood urea nitrogen		

ALP = alkaline phosphatase; ALT = alanine aminotransferase; Anti-HBc = hepatitis B core antibody; Anti-HBs = hepatitis B surface antibody; APRI = aspartate aminotransferase to platelet ratio index; AST = aspartate aminotransferase; eGFR = estimated glomerular filtration rate; GT = genotype; HBsAg = hepatitis B surface antigen; HBV DNA = hepatitis B virus deoxyribonucleic acid; HCV = hepatitis C virus; HIV = human immunodeficiency virus; INR = international normalized ratio; PT = prothrombin time; PTT = partial thromboplastin time; RBC = red blood cell; RNA = ribonucleic acid; WBC = white blood cell count.

Subjects should be fasted for all on-treatment visits to allow for appropriate PK analysis.

7.1.3.2 Pharmacokinetic/Pharmacodynamic Evaluations

The decision as to which plasma samples collected will be assayed for evaluation of PK will be collaboratively determined by the Departments of Quantitative Pharmacology and Pharmacometrics (QPP) and the appropriate department within Clinical Research. If indicated, these samples may also be assayed and/or pooled for assay in an exploratory manner for metabolites and/or additional PD markers. The time points for both PK and viral kinetic sample collection are detailed in [Table 13](#).

7.1.3.2.1 Pharmacokinetics: Blood Collection for Plasma MK-3682 (and Metabolites), and Ruzasvir

Sample collection, storage and shipment instructions for plasma samples will be provided in the operations/laboratory manual.

Sample Collection

Pharmacokinetic samples will be collected from all enrolled subjects according to the PK sampling schemes shown in [Table 13](#).

- Subjects in the Intensive PK/PD Group will be providing additional PK samples on Day 3 (pre-dose) and on Day 7 (post-dose) that are not being collected from the other subjects in the study.

Dosing and Sample Collection Instructions

- As specified previously in Section 5.2.2, Timing of Dose Administration, all doses of MK-3682 and RZR should be taken on an empty stomach after an overnight fast, at least 1 hour before the morning meal, with water but without food.
- On all PK visits where a pre-dose sample will be collected, the visit should occur prior to the subject's regular time for taking their study medication and the subject should withhold their dose until after the visit.
- For pre-dose PK visits after Visit 2 (Day 1), if this visit time is not feasible, the subject should be instructed to take their study medication as per their regular schedule. PK samples should still be collected during the visit.

Note: While every effort should be made to schedule visits with PK draws so that they occur within the window specified in [Table 13](#); when this is not possible, the PK samples should still be collected even if out of window.

- The date and time of each PK sample as well as the date and time of the last dose of MK-3682 and RZR prior to the PK sample will be recorded.

Recording and Entering Meal Information

- Subjects will be provided with a meal diary with instructions for recording meal data that includes what they eat/drink and the time of the meal. Subjects should record ALL meal data from 48 hours BEFORE the PK visit through the day of the PK visit.
- The site will be responsible for entering the appropriate data from the meal diary, as well as the qualitative fat content of the meal, in the eCRF according to the eCRF Entry Guidelines. Meal data should be entered by the site as follows:
 - For visits where only a predose PK sample is collected, enter meal data for up to **5 hours before, and up to 2 hours after** the MK-3682 and RZR dose administered on the day **prior** to the predose PK visit.
 - For visits where a postdose PK sample is also collected, also enter meal data for up to **5 hours before, and up to 2 hours after** the MK-3682 and RZR dose administered at the study site.
 - For subjects who may take multiple meals during the time window, only the meal closest to the last dose prior to the PK samples will be entered.

Table 13 Pharmacokinetic and Pharmacodynamic Sampling Time Points

Visit Number	Study Day/Week	Time Relative to Dose of MK-3682/RZR ^{1,2}	All Subjects	Intensive PK/PD Group Subjects	
			PK Time Points for MK-3682 and RZR	PK Time Points for MK-3682 and RZR	PD (Viral Kinetic) Time Points
2	Day 1	Predose	X	X	X
2-3	Day 1 – Day 2	2, 4, 8, 12, 24, and 32 hours postdose	n/a	n/a	X
4	Day 3	Predose	n/a	X ³	X
5	Day 5	n/a	n/a	n/a	X
6	Day 7	Predose	X	X ³	X
		0.5-, 2-, and 4-hour postdose	n/a	X ³	n/a
7	Week 2	Predose	X	X	n/a
8	Week 4	Predose	X	X	n/a
		0.5- and 2-hour postdose	X	X	n/a
9	Week 6	Predose	X	X	n/a
10	Week 8	Predose	X	X	n/a
12	Week 12	Predose	X	X	n/a
14	Week 16 ⁴	Predose	X	X	n/a
21	HCV/HIV Viral Failure Confirmation Visit ⁵	n/a	X ⁵	X	n/a
22	Early Discontinuation Visit ⁵	n/a	X ⁵	X	n/a

ECG = electrocardiogram; HCV = hepatitis C virus; HIV = human immunodeficiency virus; n/a = not applicable; PD = pharmacodynamic(s); PK = pharmacokinetic(s); RZR = ruzasvir.

¹ Time relative to last dose of MK-3682 and RZR must be recorded in the electronic case report form.

² After study Visit 2, if there are cases in which a morning visit is not feasible and a subject is seen in the afternoon, the subject should take their study medication in the morning, after an overnight fast, as per their regular schedule (in accordance with Section 5.2.2 Timing of Dose Administration) and PK samples will still be collected during these visits.

³ ECGs will be collected on ALL subjects on screening, Day 1, TW2, TW4, TW8, TW12, FW4 and FW12; Additional ECGs will be collected on subjects in the Intensive PK/PD Group subjects on Day 3 and Day 7.

⁴ Week 16 only applies for those subjects whose treatment duration may be extended. **PK sampling scheme for these subjects remain the same with the addition of TW16 time point.**

⁵ PK samples and meal information for PK are to be collected at HCV/HIV viral confirmation or early discontinuation visits that occur only during the study treatment period.

Note: Approximately 4 mL of blood will be collected at each specified time point for plasma PK assessment of MK-3682 (and metabolites).
 Approximately 4 mL of blood will be collected at each specified time point for plasma PK assessment of RZR.

Note: The date and time of the PK sample collection for all MK-3682 (and metabolites) and RZR PK samples must be recorded in the electronic case report form.

Note: At the time of PK sample collection, subjects will be asked to provide information regarding the time/date of the last MK-3682 and RZR dose prior to the PK sample collection. (This can also be obtained by referencing the subject's study medication diary.)

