The first dose of trial treatment will be administered at the trial site at Visit 2 (Day 1). The doses to be taken at other visits at which a pre-dose PK sample is to be collected will also be administered at the trial site. See Section 5.2.2 for specific dosing instructions. Subsequent dosing will be performed once daily by the subject (i.e., unsupervised at his/her home) at approximately the same time each day.

The investigator shall take responsibility for and shall take all steps to maintain appropriate records and ensure appropriate supply, storage, handling, distribution and usage of trial treatments in accordance with the protocol and any applicable laws and regulations.

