5.2.2 Timing of Dose Administration

MK-3682 and RZR

All doses of MK-3682 and RZR should be taken on an empty stomach after an overnight fast, at least 1 hour before the morning meal. Study medications should be taken with water but without food. In addition, subjects should fast overnight prior to reporting to the study site for dosing on Treatment Day 1 (Visit 2) and for all other visits at which a pre-dose PK sample is to be collected. For study visits after Visit 2, if there are cases in which a morning visit is not feasible and a subject is seen in the afternoon, the subject should take their study medication in the morning, after an overnight fast, as per their regular schedule and PK samples will still be collected during these visits.

If a subject misses a dose of MK-3682 or RZR and it is less than 8 hours before the next dose, the missed dose should be skipped and the normal dosing schedule resumed. Subjects should not double the next dose in order to compensate for what has been missed.

If a subject misses a dose of MK-3682 or RZR and it is greater than 8 hours before the next dose, the missed dose should be taken at least 2 hours after last meal and 1 hour before next meal and the normal dosing schedule resumed.

If for any reason MK-3682 or RZR needs to be interrupted, the entire regimen should be interrupted and can be interrupted for up to 3 days. If the interruption lasts for more than 3 days, consult the Sponsor Protocol team.

Ribavirin

Dosing of RBV should follow the approved local prescribing information.

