- ²⁰ Study medication will be dispensed at Day 1 and then every 4 weeks thereafter: Week 4 and Week 8. If the treatment regimen is extended, MK-3682 + RZR also will be dispensed at Week 12. RBV should be locally sourced and dispensed by the site if the treatment regimen is extended. Note that the duration of treatment with MK-3682 + RZR for subjects with a particular GT may be extended to 16 weeks' duration and RBV added to the regimen if the efficacy criteria for stopping enrollment/treatment allocation are met for that particular GT. For example, if efficacy criteria for stopping enrollment/treatment allocation are met for GT1-infected subjects at TW8, GT1-infected subjects already on treatment will receive MK-3682 + RZR for an additional 8 weeks (i.e., 16 weeks' total duration) + RBV for 8 weeks.

All doses of MK-3682 and RZR should be taken on an empty stomach after an overnight fast, at least 1 hour before the morning meal. Study medications should be taken with water but without food. In addition, subjects should fast overnight prior to reporting to the study site for dosing on Treatment Day 1 (Visit 2) and for all other visits at which a pre-dose PK sample is to be collected. MK-3682 and RZR (open-label) will be provided by the Sponsor to cover a maximum of 32 days of dosing (4 weeks + 4 days). An unscheduled visit must occur to get additional drug if the subject will run out of study drug prior to the next scheduled visit. If dosing is missed or interrupted (see Section 5.2.2), the assigned study therapy regimen should still be completed.

For subjects whose treatment regimen is modified to include RBV, RBV is to be dosed according to the approved local prescribing information.

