7.1.5.4 Drug Administration

Following completion of the Day 1 procedures and confirmation of eligibility, the site pharmacist or study coordinator will contact the interactive voice response system/interactive web response system (IVRS/IWRS) for assignment of the drug regimen to be administered and duration of treatment. Sites should not call IVRS for drug administration until the subject has met all criteria for the study and are ready to receive the first dose of study medication on Day 1.

The first dose of prescribed study medications should be administered at the Day 1 visit. Study medications should be taken on an empty stomach after an overnight fast, at least 1 hour before the morning meal. Study medications should be taken with water but without food. In addition, subjects should fast overnight prior to reporting to the study site for dosing on Treatment Day 1 (Visit 2) and for all other visits at which a pre-dose PK sample is to be collected. All other dosing after the Day 1 visit will be performed by the subject (i.e., unsupervised at his/her home) and recorded on the subject's SMD provided during the visit.

Subjects should complete study therapy as defined by their assigned treatment regimen and per Section 5.2.

Additional instructions related to drug administration on PK visit days are provided in Section 7.1.3.2.1.

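### The instruction to withhold the dose until the PK visit is over makes the scheduled post-dose samples at Week 4 and Day 7 impossible

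*Combined protocol and SAP*

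**What the plan says.** The bullet sits under the dosing and sample collection instructions of Section 7.1.3.2.1. It covers all PK visits with a pre-dose sample, exempts none, and says "the subject should withhold their dose until after the visit".

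Other text needs the dose to be taken during the visit:

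- **Table 13, Week 4, all subjects:** a pre-dose sample, then "0.5- and 2-hour postdose".
- **Table 13, Day 7, intensive group:** a pre-dose sample, then "0.5-, 2-, and 4-hour postdose".
- **Section 7.1.3.2.1, meal data:** for visits with a post-dose sample, sites enter meals around "the MK-3682 and RZR dose administered at the study site".
- **Section 5.2:** the dose at later visits where "a pre-dose PK sample is to be collected will also be administered at the trial site".
- **Section 5.2.2, with the same wording in flow-chart footnote 20:** subjects fast before "reporting to the study site for dosing on Treatment Day 1 (Visit 2) and for all other visits at which a pre-dose PK sample" is due.
- **Section 12.3:** 12 mL per drug at Week 4, and 4 mL (main) or 16 mL (intensive) at Day 7. Table 13 sets about 4 mL per draw.

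Section 7.1.5.4 sends sites back to the bullet's section: "Additional instructions related to drug administration on PK visit days are provided in Section 7.1.3.2.1". It also has subjects report to the site for dosing at pre-dose PK visits, then says that all other dosing after Day 1 is unsupervised at home. Section 7.1.1.8 mentions witnessed dosing only at Day 1.

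**The concern.** A sample timed 0.5 hours after the dose cannot be drawn at a visit if the dose is held until that visit ends. The bullet also fails at Day 1, which has a pre-dose sample and is where the first dose must be given. Its conflict with Section 5.2 extends to every later pre-dose PK visit, although where only a pre-dose sample is due, dosing afterwards loses no scheduled sample.

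This is an operative rule, in the section to which sites are sent for dosing on PK days. A site that obeys it loses its scheduled post-dose samples. Section 4.2.5.3 names these as inputs to the PK-safety and PK-efficacy modeling. If sites differ in which text they follow, the missing samples will be clustered by site.

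For subjects outside the intensive group, Week 4 is the only visit with scheduled post-dose PK. That includes all of the first 50, to whom Section 2.1 closes the intensive group.

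**Working it through.** **Inputs.** About 250 subjects, of whom about 30 (5 for each of 6 genotypes) are intensive (Section 2.1), leaving 220 in the main scheme. Sampling times and 4 mL per draw per drug come from Table 13; volumes come from Section 12.3. Counts run through Week 12, without the extra Week 16 sample for extended treatment.

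**Step 1: reproduce the plan's blood volumes.**

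- Main scheme: pre-dose at Day 1, Day 7 and Weeks 2, 4, 6, 8 and 12 = 7 draws, plus 2 post-dose at Week 4 = 9. Volume 9 × 4 = 36 mL per drug.
- Intensive scheme: 9 + 1 (Day 3 pre-dose) + 3 (Day 7 post-dose) = 13. Volume 13 × 4 = 52 mL per drug.

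Both equal the Section 12.3 totals of 36 and 52 mL. At Week 4, 12 / 4 = 3 draws; at Day 7 in the intensive group, 16 / 4 = 4 draws. The post-dose draws are therefore part of the plan.

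**Step 2: apply the bullet literally.** Each visit keeps only its pre-dose draw.

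| Scheme | Planned draws | Under the bullet | Lost per subject | Volume per drug under the bullet |
|---|---|---|---|---|
| Main | 9 | 7 | 2 | 28 mL |
| Intensive | 13 | 8 | 5 | 32 mL |

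**Step 3: total at target enrollment.**

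- Scheduled: 220 × 9 + 30 × 13 = 1,980 + 390 = 2,370.
- Post-dose: 250 × 2 (Week 4) + 30 × 3 (Day 7) = 500 + 90 = 590, and 590 / 2,370 = 24.9%.
- Pre-dose, not at risk: 2,370 − 590 = 1,780.
- First 50 subjects: 50 × 9 = 450 scheduled; 50 × 2 = 100 post-dose, all at Week 4; 100 / 450 = 22.2%.

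**Step 4: range of loss.** The share of subjects at sites that follow the bullet is not in the documents. The shares below are assumptions, for illustration only.

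| Assumed share | Scheduled post-dose points lost |
|---|---|
| 10% | 59 |
| 25% | 148 (147.5) |
| 50% | 295 |
| 100% | 590 |

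**Step 5: look for an exemption.** The fallback in Section 7.1.3.2.1 and footnote 2 of Table 13 apply only when the visit cannot take place at the pre-dose time. They may yield post-dose samples at other recorded times, but do not secure the scheduled 0.5- and 2-hour points, and are not counted here. No text exempts Week 4 or Day 7.

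**The case against.** The strongest reply is that the protocol largely corrects itself. Table 13, the meal rule, Sections 5.2 and 5.2.2, footnote 20 and the blood volumes all point to dosing at the site, against one loose word: visit where pre-dose draw was meant. That is a fair account of the intent. It does not rescue the instruction, because Section 7.1.5.4 directs sites to this very section.

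The second reply is that 590 is a ceiling, and this stands. The figure assumes full enrollment and no dropout, while Section 2.1 expects that genotypes 5 and 6 may not fill. The first 50 subjects complete Week 4 before the other 200 (80%) are allocated, and sample and dose times are recorded, so missing samples could be noticed by then. Under Section 7.1.3.2 the sponsor also chooses which samples are assayed. High rates of loss are therefore unlikely, but early detection would not recover samples already missed.

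Third, site behavior, and hence clustering, is conjecture: sites also have an operations/laboratory manual that is not among the documents. This is correct, and clustering is stated here only as conditional. It is also true that reliance on Week 4 applies to all of the roughly 220 subjects outside the intensive group, not specially to the first 50.

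Finally, in Section 7.1.5.4 the word other can be read as excluding the pre-dose PK visits just mentioned. That reading is available, so the sentence is ambiguous rather than a second contradiction, and editing it is optional.

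**Conclusion.** The inconsistency is real, and the bullet is wrong as written. Up to 590 of 2,370 scheduled PK time points (25%) are exposed: 500 at Week 4 and about 90 at Day 7. This rests on target enrollment, 30 intensive subjects, no dropout and no treatment extension. The actual loss lies between none and that ceiling and cannot be estimated from the documents.

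The consequence is limited to the timed post-dose data for modeling. The primary PK endpoint is the trough concentration and comes from the pre-dose samples; the SVR endpoints and the safety criteria in Section 5.11.1 use no PK. The wording should be corrected, but the error does not threaten the trial's main conclusions. Confidence is high for the textual conflict; the size of any loss is uncertain.

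**What to change.** In Section 7.1.3.2.1, replace the end of the bullet with: *withhold the dose until the pre-dose sample has been drawn; the dose is then taken at the site, and at Week 4 (and at Day 7 for the intensive group) the subject stays for the post-dose samples*. Keep the existing fallback for visits that cannot occur at the pre-dose time.

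In Section 7.1.5.4, limit the home-dosing sentence to days other than visits with a pre-dose PK sample, to match Section 5.2.

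The cost is two wording edits. The samples are already in Table 13 and Section 12.3, so no visit, draw or blood volume is added. The documents do not state whether dosing is finished. If it is, the recorded dose and sample times can be used to count the missing or mistimed post-dose samples, by site, before the modeling.
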